9.2 Target Lesions

All measurable lesions up to a maximum of 2 lesions per organ and 5 lesions in total, representative of all involved organs, will be identified as target lesions and recorded and measured at baseline. Target lesions will be selected on the basis of their size. Lesions with the longest diameter (short axis for lymph nodes) and are $\geq 10 \text{ mm}$ (CT and MRI), $\geq 15 \text{ mm}$ lymph nodes, > 20 mm CXR and are for accurate repetitive measurements (either by imaging techniques or clinically) will be chosen. A sum of the longest diameter (short axis for lymph nodes) of all target lesions will be

calculated and reported as the baseline sum diameters. This will be used as reference to further characterize the objective tumor response of the measurable dimension of the disease.

The above standard RECIST technique will be used for measurement of the longest diameter of the target lesion.

NOTE: We will use I-PDT and PDT to treat *extrabronchial and endobronchial tumors*. The *extrabronchial* will be treated with EBUS-TBN I-PDT. *The endobronchial tumors (inside the airway) can be treated with* I-PDT and/or PDT. All treated tumors will be measured by CT scans (baseline and follow-up).

Tumors that are *inside* the airway that will be treated with laser, rigid bronchoscopy or ablation (see Section 6), *will not be measured on CT scan*.

Therefore, the volume of the tumor that will be treated with either EBUS-TBN I-PDT or with I-PDT and/or PDT will be measured on CT that was performed within 2 weeks ± 1 week before the procedure (refer to Section 8.1: Baseline Evaluations) will be compared to the volume of the I-PDT and PDT treated tumor on CT that is taken at initial follow-up bronchoscopy (refer to Section 8.1.5).

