8.1.8 Initial Follow-Up Evaluation

The following evaluations will be performed **4 weeks** (± **1 week**) after the last study I-PDT and/or PDT (*unless otherwise indicated**):

- Physical examination (including vital signs)
- Hematology: Complete blood count (CBC) with automated differentials.
- Chemistry: Complete metabolic panel (CMP).
- Blood draw for immune markers
- ECOG Performance Status (Appendix A)
- Tumor/Disease Assessment: Chest CT scan
- Concomitant medications
- Quality of Life Questionnaire (Cohorts A and B; Appendix D)
- Adverse events (will be followed for 30 days following treatment/procedure)
- Schedule date/time for follow-up bronchoscopy with EBUS (without TBNA). TBNA will be performed only if clinically indicated outside the scope of this study. If a tumor is visible, tumor tissue biopsies (about 50-300 mg per biopsy, if feasible) will be collected for immune markers. NOTE: The bronchoscopy will not be performed at this visit.
- If EBUS is performed and a tumor is visible, tumor tissue biopsies (about 50-300 mg per biopsy, if feasible) will be collected for immune markers.

*Bronchoscopic and ultrasound images that are routinely obtained during therapeutic procedures will be used to evaluate the airway initially and during follow up. *Note: Initial follow-up bronchoscopy will be performed within 4 weeks following the first follow-up visit. Additional bronchoscopies will be performed as clinically indicated.*

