8.1.11 Schedule of Procedures and Observations

The schedule of procedures and observations for this study is summarized in Table 1 below.

Evaluation	Baseline ¹	Day -3	Day -2	Day -1	Scheduled EBUS I- PDT (Day 0)	Days 1 through 3	Days 2 through 10 ²²	7-10 Days Post- Procedure	Initial Follow-Up ² Evaluation	Long Term Follow-Up ³ Evaluation s
Medical History	Х									
Pre-Existing Conditions	Х									
Physical Examination, including vital signs ⁴	Х				X ⁵		X ^{5,22b}		X	Х
Hematology ⁶	Х		X ²⁴		X ²⁴				X	
Blood Chemistry/creatinine clearance ⁷	Х		X ²⁴		X ²⁴				X	
Pregnancy Test (Urine/Serum)	X^8									
ECOG Performance Status (Appendix A)	Х								X	Х
Tumor/Disease Assessment: Contrast Enhanced CT scan (chest) ⁹ (non-contrast CT if the patient has allergy to the contrast agent)	X9								X9	X9
Injection of porfimer sodium			X							
Diet prior to I-PDT procedure					X ²⁰		X ^{20a}			
Cohort B Only: SOC palliative radiotherapy			X ²²							
SOC Bronchoscopy/EBUS- TBNA					X ¹⁰				X ¹¹	
EBUS color Doppler to identify vasculature					Х					
Tumor Debulking, Ablation and/or Airway Stenting					Х		X			

Table 1Schedule of Procedures and Observations

Evaluation	Baseline ¹	Day -3	Day -2	Day -1	Scheduled EBUS I- PDT (Day 0)	Days 1 through 3	Days 2 through 10 ²²	7-10 Days Post- Procedure	Initial Follow-Up ² Evaluation	Long Term Follow-Up ³ Evaluation s
If possible, optical and pO2 measurements immediately before and after I-PDT					X ²³					
I-PDT ¹² guided with EBUS- TBN and/or I-PDT and/or PDT					X					
Immune marker blood and tumor tissue sampling ¹³			X		Х			Х	Х	
Pre-I-PDT and/or PDT tissue sample					X ^{14,14a}		X ^{14b}		X ¹⁴	
Concomitant Medications	X ¹⁵				Х		X ^{22b}		Х	X ¹⁶
Adverse Events					X		X ^{22b}		Х	
Quality of Life Questionnaire (Appendix D) ¹⁷	Х								Х	X ¹⁸
Six-Minute Walk Test ²¹	Х									X ¹⁸
Survival Status										X ¹⁹

1 Performed within 4 weeks prior to scheduled EBUS I-PDT, as part of standard of care for the therapeutic bronchoscopy, unless otherwise indicated.

2 Initial Follow-Up evaluation at 4 ± 1 weeks after the last I-PDT and/or PDT treatment (dependent on severity of disease and clinical condition of patient).

3 Long-Term Follow-Up routine will be performed only when clinically indicated, at these visits: 8 weeks (± 2 weeks), 12 weeks (± 2 weeks), and 24 weeks (± 4 weeks) after the last I-PDT and/or PDT.

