9 EFFICACY EVALUATIONS

9.1 **Objective Tumor Response**

All protocol-defined imaging studies must be performed at the investigative site or sponsorapproved facility using protocol-defined parameters. The same method of assessment and the same technique should be used to characterize each identified and reported lesion at baseline and during follow-up. A modified RECIST 1.1 criterion will be used to assess objective tumor response of the I-PDT and/or PDT treated tumor.

RECIST 1.1 will be used for tumor response assessment at time of continuing review and will be used for IRB reporting and formal analysis.

Along with tumor size and volume, percent of airway obstruction (in cases where an airway stent is not placed) measured by bronchoscopy, will also be used as a measure of tumor response.

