9.2.1 Evaluation of Target Lesions

Tumor response assessments will be performed at 4 weeks (\pm 1week) following I-PDT and/or PDT (refer to Section 8.1.8).

- Complete Response (CR): Disappearance of all target lesions.
- **Partial Response (PR):** At least a 30% decrease in the sum of diameters of target lesions, taking as reference the baseline sum diameters.
- **Progressive Disease (PD):** At least a 20% increase in the sum of diameters of target lesions, taking as references the smallest sum on study (this includes the baseline sum if that is the smallest on study). In addition to the relative increase of 20%, the sum must also demonstrate an absolute increase of at least 5 mm.
- Stable Disease (SD): Neither a sufficient shrinkage to qualify for PR nor sufficient increase to qualify for PD, taking as reference the smallest sum diameter while on study.

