12.1.3 Primary Phase II Efficacy Analysis

The primary endpoint for Cohort A and Cohort B is the proportion of complete responders (CR) and partial responders (PR) as measured by RECIST v1.1 at 12 ± 1 week after DOSIETM (Cohort A) and COMSOLTM guided I-PDT.

For Cohort A, we hypothesize that the objective tumor response for CR+PR will be at least 29%. We also want to investigate the impact of variation in optical properties, Photofrin® retention, and fiber location perturbation on the objective tumor response. The primary analysis will consist of a one-sided exact binomial test of H₀: π =0.05 versus H_a: π >0.05 at level α =0.05, where π is the proportion of CR+PR responders. For Cohort B, the primary analysis will consist of a one-sided exact binomial test of H₀: π =0.30 versus H_a: π >0.30 at level α =0.05.

Additional clinical efficacy endpoints are: (1) changes from baseline to 3 months in the FACT-L Total Score related subscales (physical well-being, social/family well-being, emotional well-being, functional well-being); (2) the 6-minute walk measures (distance, VO2max, shortness of breath scores). All key clinical efficacy outcomes will be considered suitably continuous will be analyzed with an analysis-of-covariance (ANCOVA) approach regressing change from baseline to three months on the baseline value of the respective measure adjusted for baseline tumor volume, age, and sex.

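### The primary CR+PR endpoint has two conflicting lesion sets, all involved organs or the treated tumour only, and the scheduled chest CT supports only the second

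*Combined protocol and SAP*

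**What the plan says.** **All-organs set.** Section 9.2 states that up to two "lesions per organ and 5 lesions in total, representative of all involved organs, will be identified as target lesions". Selection is by size, and nothing requires the treated tumour to be among them. Section 9.2.1 defines CR as "Disappearance of all target lesions" and PR as a fall of at least 30% in the sum of their diameters. Section 9.1 says that "RECIST 1.1 will be used for tumor response assessment at time of continuing review and will be used for IRB reporting and formal analysis". Section 12.1.3 says that the primary endpoint "is the proportion of complete responders (CR) and partial responders (PR) as measured by RECIST v1.1 at 12" weeks, with a one-week window.

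**Treated-tumour set.** Section 9.1 also says that "A modified RECIST 1.1 criterion will be used to assess objective tumor response of the I-PDT and/or PDT treated tumor". Section 9.2 adds that "All treated tumors will be measured by CT scans (baseline and follow-up") and compares the volume of the treated tumour before and after the procedure. Section 8.1.10 names modified RECIST 1.1 for response, and section 9.2.4 counts progression at the treated site. No section says what the modification is.

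**Imaging.** The baseline tumour assessment in section 8.1.2 is a chest CT. Section 8.1.8 lists "Tumor/Disease Assessment: Chest CT scan" at week 4, and section 8.1.9 lists a chest CT at weeks 8, 12 and 24. The imaging row of Table 1 reads "Contrast Enhanced CT scan (chest)". Footnote 9 of that table makes the follow-up CT conditional on clinical need. No other body region is scheduled at any visit.

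**The concern.** CR+PR is tested in single-arm cohorts against fixed null rates of 5% (Cohort A) and 30% (Cohort B). With no control arm, the choice of lesions feeds straight into the result. Two analysts reading different sections could build different sums for the same patient.

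Extrathoracic disease is foreseeable. Section 5.1 admits other malignancies that obstruct the airway, and neither 5.1 nor 5.2 excludes distant disease. Section 1.1.10 describes earlier patients at stages IIb to IVb, including melanoma and endometrial cancer metastatic to the airway. If a site records such a lesion as a target from imaging done outside the schedule, the protocol arranges no repeat measurement, and no rule covers an incomplete sum. Section 4.1.4 expects up to 32 patients from external sites, so practice may also differ between sites.

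**Working it through.** **1. Which lesion set can the schedule deliver?**
- *Treated tumour.* It is measured on the baseline chest CT and on each follow-up chest CT that is done. Both sums come from the same lesions.
- *All involved organs.* A lesion outside the chest field has no scheduled scan at baseline or at weeks 4, 8, 12 and 24. If nobody measures it at baseline, the 9.2 requirement is unmet, but a chest-only sum still exists. If it was measured on unscheduled imaging, the follow-up sum may be incomplete.

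So the schedule fits the treated-tumour set and does not secure the all-organs set.

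**2. Does the choice matter when every lesion is rescanned?** Take a hypothetical 50 mm treated tumour and an unchanged 25 mm untreated lesion.
- Treated-tumour set: PR needs a 30% shrinkage of the tumour.
- All-organs set: PR needs a fall of 0.30 × (50 + 25) = 22.5 mm, which is 22.5/50 = 45% of the treated tumour. CR is impossible while the other lesion persists.
- If the 25 mm lesion were dropped at follow-up and the tumour had not changed, the sum would go from 75 to 50 mm. That is 25/75 = 33%, a false PR.

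**3. The plan's own figures (section 12.1.6).** Inputs: one-sided exact binomial test at 0.05; n = 18, null 0.05, detectable rate 0.29; n = 39, null 0.30, detectable rate 0.50; power 0.80 for both. The critical value r is the smallest with P(X ≥ r | n, null) ≤ 0.05.
- Cohort A: r = 4, actual level 0.0109, power 0.812 at 0.29. Power 0.80 is reached at a rate of 0.285.
- Cohort B: r = 17, actual level 0.04998, power 0.832 at 0.50. Power 0.80 is reached at a rate of 0.491.

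Both stated detectable rates reproduce, with Cohort B slightly conservative from rounding.

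**4. Illustration of unscorable patients.** The documents do not give the share u who cannot be scored; 10% to 40% is an assumption. If they count as non-responders, the effective rate is p(1 − u), and power is P(X ≥ r | n, p(1 − u)).

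| u | A: rate | A: power | B: rate | B: power |
|---|---|---|---|---|
| 0 | 0.290 | 0.812 | 0.50 | 0.832 |
| 10% | 0.261 | 0.730 | 0.45 | 0.630 |
| 20% | 0.232 | 0.629 | 0.40 | 0.381 |
| 30% | 0.203 | 0.512 | 0.35 | 0.169 |
| 40% | 0.174 | 0.385 | 0.30 | 0.050 |

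At 40%, the Cohort B rate equals its null, so power equals the test level.

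If these patients are excluded instead and r is recomputed:

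| u | A: n, r | A: power | B: n, r | B: power |
|---|---|---|---|---|
| 20% | 14, 3 | 0.819 | 31, 15 | 0.640 |
| 40% | 11, 3 | 0.661 | 23, 12 | 0.500 |

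Cohort A loses nothing at 20% because r drops from 4 to 3 and the actual level rises from 0.0109 to 0.0301.

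**The case against.** A reader might infer that patients with extrathoracic disease cannot be scored at all and that no rule covers them. The documents do not support that. Section 9.1 applies modified RECIST 1.1 to the treated tumour, and 8.1.10, 9.2 and 9.2.4 are consistent with it. On that reading these patients are scored from chest CT like any others. The baseline scan is also chest-only, so an extrathoracic lesion enters the sum only through measurement outside the schedule. Section 9.2.2 accepts MRI and clinical examination, so follow-up of such a lesion is possible, though not ensured. The false PR above would also breach the instruction in 9.1 and 9.2.2 to assess each recorded lesion by the same method at baseline and follow-up.

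A reader might also take 0.39 and 0.05 as the power that the trial will have. That is not supported either. The 10% to 40% share has no source in the documents, and no section says that unscorable patients count as non-responders. Exclusion gives much milder figures.

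All of this stands, and it limits the claim. It does not remove the conflict: 9.1 and 12.1.3 assign RECIST 1.1, without the word modified, to the formal and primary analysis, and the only written selection rule is the all-organs rule in 9.2.

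**Conclusion.** The point holds as an internal inconsistency in the primary endpoint. The protocol carries two lesion sets, does not define the modified criterion that would choose between them, and schedules imaging that supports only the treated-tumour set. The all-organs rule cannot be reliably followed with the planned scans. A patient with an extrathoracic target lesion measured at baseline may have an incomplete follow-up sum.

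The size is unknown. The power losses are conditional on the all-organs rule governing, on an assumed share of 10% to 40%, and on non-responder scoring. With the treated-tumour set, the lesion-set problem costs no power: the design keeps 0.812 in Cohort A and 0.832 in Cohort B, provided that the follow-up CTs are done. Footnote 9 leaves that last condition open.

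**What to change.** - In 9.2, delete the clause that requires target lesions to represent every involved organ. State that the target lesions for the primary endpoint are the treated tumour or tumours measured on chest CT, and that baseline and follow-up sums use the same lesions.
- Define this as modified RECIST 1.1 and use the term consistently in 8.1.10, 9.1, 9.2.1 and 12.1.3.
- Reconcile footnote 9 of Table 1 with the CT visits listed in 8.1.8 and 8.1.9.
- State how a patient without a scorable follow-up sum is counted.

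Limiting targets to the chest field while keeping selection by size would not be enough. Untreated chest lesions could still enter the sum and dilute the treated-tumour response that 9.1 describes. If whole-body RECIST 1.1 is really intended, matching imaging must be scheduled at baseline and follow-up.

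The recommended change costs a few sentences and adds no scan to those already listed. Its downside is that response then describes local control only, and untreated disease does not enter it.

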9.2.1 Evaluation of Target Lesions

Tumor response assessments will be performed at 4 weeks (\pm 1week) following I-PDT and/or PDT (refer to Section 8.1.8).

- Complete Response (CR): Disappearance of all target lesions.
- **Partial Response (PR):** At least a 30% decrease in the sum of diameters of target lesions, taking as reference the baseline sum diameters.
- **Progressive Disease (PD):** At least a 20% increase in the sum of diameters of target lesions, taking as references the smallest sum on study (this includes the baseline sum if that is the smallest on study). In addition to the relative increase of 20%, the sum must also demonstrate an absolute increase of at least 5 mm.
- Stable Disease (SD): Neither a sufficient shrinkage to qualify for PR nor sufficient increase to qualify for PD, taking as reference the smallest sum diameter while on study.

9.2.2 Guidelines for Evaluation of Measurable Disease

All measurements should be taken and recorded in metric notation. All baseline evaluations should be performed as closely as possible to the beginning of treatment and never more than 4 weeks before the beginning of the treatment.

The same method of assessment and the same technique should be used to characterize each identified and reported lesion at baseline and during follow-up. Imaging-based evaluation is preferred to evaluation by clinical examination unless the lesion(s) being followed cannot be imaged but are assessable by clinical exam.

• Contrast-Enhanced CT: This guideline has defined measurability of lesions on CT scan based on the assumption that CT slice thickness is 5 mm or less. If CT scans have slice thickness greater than 5 mm, the minimum size for a measurable lesion should be twice

the slice thickness. MRI is also acceptable in certain situations (e.g., for body scans). Non-contrast CT can be used if the patient has allegory to the contrast agent.

• Endoscopy, Laparoscopy: The utilization of these techniques for objective tumor evaluation is not advised. However, such techniques may be useful to confirm complete pathological response when biopsies are obtained or to determine relapse in trials where recurrence following complete response (CR) or surgical resection is an endpoint.

9.2.3 Evaluation of Airway Obstruction

The estimated percentage of obstruction will be documented before and after endobronchial debulking and ablation. Tumor debulking and ablation will always be performed before EBUS-TBNA. The airway obstruction severity is usually estimated based on the size of scope that can be passed through an obstructed airway and based on the size of the balloon used to dilate the obstructed airway.

Airway obstruction severity will be classified as follows (51):

- Mild (<50%),
- Moderate (50-70%) and,
- Severe (>70%).
- The baseline obstruction to be used in the study will be the airway obstruction that was established after debulking and ablation and, before the EBUS-TBN guided I-PDT, and/or I-PDT and/or PDT.

9.2.4 Progression-Free Survival

PFS, using modified RECIST 1.1 criteria, is defined in this study as the time from date of study treatment to the time of first observed disease progression at the treated tumor site or, death due to any cause.

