2 RATIONALE

Chemotherapy remains the mainstay of treating inoperable malignant airway obstruction. Despite chemotherapy with one or more regimens, most patients will suffer recurrent disease and may present with airway obstruction. Some patients may develop respiratory symptoms (e.g., dyspnea, hemoptysis, post-obstructive pneumonia, respiratory failure) secondary to tracheal or bronchial obstruction. Palliation of their symptoms is usually accomplished by tumor irradiation or bronchoscopic intervention. For some patients, palliative radiation results in clinical improvement after partial or complete resolution of the airway obstruction. However, other patients may have no response to radiation, which results in disease progression and worsening of respiratory symptoms.

Bronchoscopic intervention leads to faster improvement but requires an advanced bronchoscopic procedure using laser, cryotherapy, tumor debulking, and ablation with or without airway stenting. Patients at this terminal stage tend to progress with recurrent airway obstruction, which can lead to repetitive palliative bronchoscopic procedures. There is an urgent need to offer these frail patients a treatment with minimal toxicity and morbidity, and that can reduce tumor-induced symptoms with a chance to improve their quality of life and perhaps their survival.

Multiple studies have shown that PDT can lead to tumor regression in lung cancer and other malignancies when the tumors are less than 1 cm in thickness. However, I-PDT is required to treat large tumors. In recent review papers, we highlighted future directions using I-PDT with treatment planning as a possible modality to treat patients with locally advanced cancer including intrinsic and extrinsic cancer that compromise the airway and are larger than 1 cm (22, 23). In these tumors, EBUS can be used to guide the insertions of the TBN into the tumor and the RD250 laser fiber can be inserted through that needle for intra-tumor illumination (Figure 1 and Figure 2). Recently, [name] (Co-Investigator) and his research team published the concept of using EBUS-TBN to guide I-PDT in the treatment of locally advanced lung cancer. (90) In addition, I-PDT and/or PDT can be used to treat endobronchial tumors. (22)

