12.1.4 Secondary Analysis

For both Cohort 0+A combined and Cohort B progression free survival (PFS) will be defined as the time from date of study treatment to the time of first observed disease progression (modified RECIST 1.1 criteria) at the treated tumor site or death due to any cause. PFS will be summarized using standard Kaplan-Meier methods, with median PFS and specified PFS rates estimated with 95% confidence intervals. The number of bronchoscopies will be summarized descriptively.

For Cohort A only we will measure agreement between DOSIETM and COMSOLTM treatment planning measures in n=18 subjects consisting of light intensity from each fiber (mW, and mW/cm), percent of tumor that receives ≥ 8.6 mW/cm² and ≥ 45 J/cm², the irradiance and fluence at the margins, the min, average and maximum irradiance and fluence in 100% of the tumor using the concordance correlation coefficient (76)(CCC) and Bland-Altman plots (77) for visual displays of agreement. We will calculate the one-sided 95% confidence interval for the CCC using a percentile bootstrap-t approach for each endpoint and we will calculate the 95% confidence interval display. Disagreement on a given measure will be inferred if the estimated CCC is below the lower bound of the one-sided 95% percentile confidence interval.

Tumor response as a function of STAT3 tumor conversion percentages (if possible) will be analyzed using logistic regression adjusted for age and sex.

The data from this trial will inform the design of a prospective Phase IIb randomized trial.

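### PFS has no rule for repeat bronchoscopic intervention at the treated site, so airway re-obstruction is not made an event and PFS can be overstated

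*Combined protocol and SAP*

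**What the plan says.** - **Events.** Section 9.2.4 ends PFS at "first observed disease progression at the treated tumor site or, death due to any cause". Section 12.1.4 has the same list: "first observed disease progression (modified RECIST 1.1 criteria) at the treated tumor site or death due to any cause".
- **Progression.** Section 9.2.1 defines it as "At least a 20% increase in the sum of diameters of target lesions, taking as references the smallest sum on study", plus an absolute rise of at least 5 mm. The word modified is not explained for progression.
- **Obstruction.** Section 9.1 also uses bronchoscopic percent obstruction as a response measure where no stent is placed. Section 9.2.3 grades obstruction as mild, moderate or severe. Neither gives a change that counts as progression.
- **Expected course.** Section 2 says: "Patients at this terminal stage tend to progress with recurrent airway obstruction, which can lead to repetitive palliative bronchoscopic procedures". The same section closes with a hypothesis of slower progression and longer palliation.
- **Follow-up.** On bronchoscopy, section 8.1.8 says: "Additional bronchoscopies will be performed as clinically indicated". Section 4.1 places a chest CT before the planned repeat bronchoscopy. Follow-up visits are at weeks 4, 8, 12 and 24 (8.1.8, 8.1.9), and Table 1, footnote 9, makes the CTs at those visits conditional on clinical indication.
- **Analysis.** Section 12.1.4 says: "PFS will be summarized using standard Kaplan-Meier methods, with median PFS and specified PFS rates estimated with 95% confidence intervals". For repeat procedures it says only: "The number of bronchoscopies will be summarized descriptively".

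**The concern.** PFS is the plan's only time-to-event measure of the longer palliation it hopes to show, and the failure that section 2 leads one to expect has no place in it. A patient whose treated airway closes again and is reopened may be counted as progression-free, censored, or called progressed on the investigator's reading. The text does not choose between these.

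The first option credits event-free time to a patient in whom local control has failed. The second is not neutral either, because a patient with regrowth is unlikely to have the same outlook as those who remain at risk. Section 12.1.4 says the data will inform a randomised Phase IIb trial, so a flattering PFS rate could carry over into its planning assumptions.

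**Working it through.** The plan states no PFS rate, median, event count or power, so there is no figure of its own to reproduce. The check is a reading of the rules, followed by illustrations on assumed rates.

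**1. Following one patient through the rules.** Endobronchial tumour at the treated site regrows after week 12 and is debulked at week 18 at an unscheduled bronchoscopy.
- The CT that section 4.1 requires belongs to the planned repeat bronchoscopy. No text requires one before this procedure.
- No scheduled visit falls between weeks 12 and 24.
- If the week 24 CT, taken after removal, shows a sum less than 20% or less than 5 mm above the smallest sum, 9.2.1 gives no progression.
- The patient is alive, so neither listed event has occurred by week 24.

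Had the airway been stented or dilated instead, no tumour would have been removed and CT growth would remain measurable. The re-obstruction itself would still not be an event on the day it was treated.

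**2. Direction.** Let T be time to RECIST progression or death, and R time to first re-intervention for regrowth or re-obstruction. An analysis that counts both uses min(T, R), which is never later than T. Compared with that analysis, the current definition can only give equal or longer PFS.

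**3. Size, first illustration.** Assumed, not in the documents: independent exponential times, 50% local failure and 30% death by week 24, a CT at every visit, and a share q of local failures cleared before any CT shows them and never seen again (permanent masking).
- Re-intervention counted: 24-week PFS = 0.70 × 0.50 = 0.35; 12-week PFS = √0.70 × √0.50 = 0.837 × 0.707 = 0.59.
- As written: 24-week PFS = 0.70 × (0.50 + 0.50q); 12-week PFS = 0.837 × (0.707 + 0.293q).
- If cleared tumour can regrow at the same hazard and is masked again with probability q, 24-week PFS as written = 0.70 × 0.50^(1−q).

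| q | 12 weeks, permanent masking | 24 weeks, permanent masking | 24 weeks, regrowth allowed |
|---|---|---|---|
| 0 | 59% | 35% | 35% |
| 0.2 | 64% | 42% | 40% |
| 0.4 | 69% | 49% | 46% |
| 0.6 | 74% | 56% | 53% |

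The 24-week excess is 7, 14 and 21 points with permanent masking, and about 5, 11 and 18 points with regrowth.

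**4. Size, second illustration.** Assumed: median time to growth 12 weeks, median survival 26 weeks, and a share f of first growths cleared once before the next CT, with later regrowth (400,000 simulated patients).

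| f | 12-week PFS as written | 24-week PFS as written |
|---|---|---|
| 10% | 39.0% | 15.0% |
| 25% | 42.7% | 17.8% |
| 50% | 48.9% | 22.4% |

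With re-intervention counted, the values are 36.4% at 12 weeks and 13.2% at 24 weeks for every f.

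**5. Omission without erasure.** If re-interventions arise independently of RECIST events in a share r by week 24, PFS counting them = current PFS × (1 − r). From an assumed 50%, r of 10%, 20%, 30% and 40% gives 45%, 40%, 35% and 30%. Independence is a simplification, since re-obstruction and CT growth are likely to be related.

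**The case against.** The strongest reply is that the plan is less closed than its event list suggests, and that PFS has limited weight.

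- **Obstruction is a response measure.** A reader might infer that re-obstruction is expressly excluded from PFS. Sections 9.1 and 9.2.3 do not support that: percent obstruction is recorded and used for response, and the RECIST modification is left open. What remains is a missing rule. No threshold is given, stented airways are left out of the measure, and 9.2.2 advises against endoscopy for objective tumour evaluation, apart from confirming complete response or detecting relapse in certain trials.
- **Treated tumours stay on CT.** Section 9.2 says some tumours inside the airway are not measured on CT, and a reader might infer that a treated lesion leaves CT follow-up once it is debulked. The sentence concerns tumours managed by laser, rigid bronchoscopy or ablation, and the paragraph before it keeps all I-PDT- and PDT-treated tumours on CT at baseline and follow-up. That inference fails.
- **A CT may come first.** Section 4.1 secures this for the planned repeat bronchoscopy, and symptomatic re-obstruction may itself prompt a CT. This narrows erasure to unscheduled procedures without a prior scan.
- **Much tumour cannot be erased.** Endobronchial debulking leaves extrabronchial tumour measurable, and a lower smallest sum makes later progression easier to reach. Both points stand, though progression reached that way would still be dated after the re-obstruction.
- **Bronchoscopies are counted.** A count gives neither the timing nor the reason, so it cannot replace an event date.
- **PFS is descriptive, and re-intervention is a discretionary, unblinded decision.** Both are true. They argue against replacing the current definition outright, but not against a second prespecified analysis.

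**Conclusion.** The concern holds as a gap in the endpoint rules. No rule makes re-obstruction or repeat intervention at the treated site a PFS event, and none says how to handle it. Where endobronchial regrowth is debulked or ablated without a prior CT, later scans can conceal it and PFS is overstated as a measure of local control. For stenting or dilation, the failure is simply not counted when it occurs.

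The direction follows from the definitions. The size does not: the 42% to 56% against 35% rests wholly on assumed failure, death and masking rates with permanent masking, and it shrinks if regrowth is allowed. No primary test, significance level or sample size is affected.

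A reader might also infer from section 1.1.10, where 3 of 10 earlier patients were alive at 8.3, 12 and 26.5 months, that deaths dominate the composite. Those figures give no 24-week death rate and do not show this.

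**What to change.** In 9.2.4 and 12.1.4:

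1. Prespecify a PFS analysis, reported beside the current one, in which the first bronchoscopic re-intervention for documented tumour regrowth or tumour re-obstruction at the treated site is a local progression event dated at the procedure. Planned early debulking, debris clearance and planned stenting do not count. Define the early window in the text itself, because the footnote number on Table 1's Days 2 through 10 column leads to the radiotherapy note.
2. State that CTs taken after tumour removal at the treated site are not used to show absence of progression.
3. State whether the 9.1 obstruction measure can trigger progression under modified RECIST and, if so, at what change.
4. Record the date and reason of each post-treatment bronchoscopy.
5. Report cumulative incidence of local failure with death as a competing event.

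The cost is protocol and SAP wording, plus two data items for procedures already counted as a secondary endpoint. The drawbacks are a less favourable PFS figure in the added analysis and some reliance on the operator's stated reason for the procedure. Treatment, sample size and the primary tests do not change.
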